## **5.0 Study Procedures**

### **5.1 Study Design**

Participants in this research study will be men and women, age 18 to 80 years, who are able to walk without the assistance of an aid. People with and without ankle OA, will be enrolled. Targeted enrollment by ankle OA status and alignment type is listed in the table below. Vulnerable populations will not be specifically targeted for enrollment. See inclusion/exclusion criteria below in section 5.4.

Study Groups	Varus Misalignment	Neutral Alignment	Valgus Misalignment
up to 30 – Controls, no ankle OA	0	30	0
Up to 120 - People with Ankle OA	40	40	40

See section 5.5 below for data collection procedures and risk management.

## 5.2 Recruitment Methods and Initial Screening

Up to 3000 individuals may be approached during recruitment and enrollment procedures. Please note that all references in this section to in-person contact/initial-screening will follow the *Talking Points* attachment, all phone calls for contact/initial-screening will follow the *Phone Script* attachment, all references to approach letters and postcards refer to the *Recruitment Letter* attachment.

### Recruitment activities at the VA

#### CPRS and Letter/Phone/In-person

Designated study staff will screen the relevant VA Puget Sound (Seattle and American Lake) clinic lists and attend clinic at the VA Puget Sound facilities to identify potential participants with a qualifying ankle OA diagnosis. Before or after clinic, study staff will discuss with the clinician any patients that might be appropriate candidates. If the clinician agrees that the patient may be an appropriate study participant, the clinician will ask the patient if she/he is interested in speaking with study staff; patients will be given a chance to opt out. For patients who are interested, study staff will speak to potential participants directly during or after a clinic visit and/or use CPRS to obtain potential participants' contact information (i.e., name, address, telephone number). For potential participants who learned about the study in person, study staff may make a follow-up approach phone call and/or send an approach letter to potential participants asking whether they are interested in finding out if they are eligible for the study. If potential participants are unable to meet with designated study staff in person then we will send an approach letter to them asking whether they are interested in participating. We may also search CPRS to identify individuals with a qualifying ankle OA diagnosis and mail them the approach letter. If potential participants have not spoken with us within 30 days of the first call and/or mailing the approach letter, study staff will contact them by phone up to two more times about this study. The approach letter will also include an "opt out" postcard. The opt-out postcard will have a unique study recruitment identification code of the form "IDCTd1", "IDCTd2" etc. where the letters IDCT are an abbreviation for "Improving the Detection, Classification and Treatment", the letter d indicates the contact information came from the database, and the

appended number is based on the order in which the postcard was mailed. If an individual returns the postcard to opt out they will not be approached about this study again.

#### Database and Letter/Phone/In-person

Designated study staff may also identify potential participants using the VA Center for Limb Loss Prevention and Prosthetic Engineering Subject Registry (PI: [name], #00433). The Registry contains contact information for participants who were screened for and/or participated in previous studies with our research group and agreed to be contacted for future studies. Study staff may make an approach phone call and/or send an approach letter to potential participants asking whether they are interested in the study. If potential participants have not spoken with us within 30 days of the first call and/or of the mailing the approach letter, designated study staff will contact them by phone up to two more times. The approach letter will also include an “opt out” postcard. The opt-out postcard will have a unique study recruitment identification code of the form “IDCTr1”, “IDCTr2” etc. where the letters IDCT are an abbreviation for “Improving the Detection, Classification and Treatment”, the letter r indicates the contact information came from our Registry, and the appended number is based on the order in which postcard was mailed. If an individual returns the postcard to opt out they will not be approached about this study again. Designated study staff may also speak with participants in the registry about this study during a clinic visit if an individual has an appointment at the VA.

The link between the study recruitment identification code and individuals’ contact information will be kept in a password protected electronic document at the VA Puget Sound (Seattle) in a restricted access folder. Hard copies of screening documents will be labeled with the ID code and stored in a locked cabinet at the VA Puget Sound.

#### Print/Text/Online/Flyers/Newsletter

We may post classified ads in print and online publications (*see Recruitment Ad Text attachment*). We may also post the classified ad text to our Center’s webpage.

We will also post flyers (*see Recruitment Flyers*) at the VA Puget Sound (Seattle and American Lake) so that interested potential participants can contact us about the study. The flyers will also be presented/posted via the VA’s closed caption TV system. We may also post flyers in publicly accessible locations in the community such as public library community boards, community center information boards, and coffee shops.

We may also include recruitment information in our center newsletter.

#### VAPSHCS Research Week

Designated study staff will host an information table during the VA Puget Sound Healthcare System Research Week. Study flyers and informational posters will be posted at the information table. If study staff identify any Research Week attendees as potential study participants, they may approach

the attendee about participating in the research study. If the attendee is interested in learning more about the study, study staff may screen the attendee for qualifying criteria.

### **Recruitment Activities at UW/Harborview**

A confidentiality agreement will be obtained for this activity; the UW does not consider itself “engaged” for the recruitment activity described below, please see attached engagement worksheet.

Designated study staff will screen relevant UW/Harborview clinic lists, appointment calendars and patient medical records to identify potential participants with a qualifying ankle OA diagnosis. Study staff will also attend clinic at these facilities to identify and/or contact potential participants. Before or after clinic, study staff will discuss with the clinician any patients that might be appropriate candidates. If the clinician agrees that the study may be a good fit for a patient, the clinician will ask the patient if she/he is interested in speaking with study staff. For patients who are interested, study staff will speak to potential participants directly during/after a clinic visit to tell them about the study, give them a study flyer, and/or request their permission to screen them for initial eligibility (via the VA IRB approved In-Person Talking Points) and provide this information to the VA. If potential participants are screened for initial eligibility in person using the In-Person Talking Points, study staff will label the noted responses with a recruitment id code and no HIPAA identifiers or sensitive health information will be noted on the form. Study staff will transport the forms to the VA for storage. If patients are interested in learning about the study and/or in doing the initial screening but are unable to meet in person with study staff, we will look up the patients’ contact information in their medical record and contact them on the phone and/or send them the VA recruitment letter (the VA IRB approved letter with VA contact information would be sent per the process described above). Staff will also search/access UW medical records to identify individuals with a qualifying ankle OA diagnosis, obtain their contact information (i.e., name, address, telephone number) and mail them the approach letter.

Also, for potential participants who were initially contacted via letter and/or in-person but have not yet completed the initial screening, study staff may provide the potential participants’ contact information and limited pre-screening criteria over the phone to other study staff at the VA who will enter it into the screening log for tracking and follow up. This information may also be added (via VA remote access) to the screening log maintained on the VA server. Study staff will follow up with potential participants based on the VA approved protocol. Consent and all data collection procedures will be conducted by approved research staff at the VA Puget Sound.

### **5.3 Informed Consent Procedures**

A waiver of informed consent and HIPAA authorization will be used for recruitment and screening purposes. A waiver of documentation of consent and HIPAA authorization will be used in order to retain the preliminary eligibility screening responses (*see Talking Points and Phone Script*). Informed consent will be obtained prior to enrollment in the study.

Designated study staff and/or the PI will conduct the informed consent process. All study personnel will complete the necessary human subjects' protections training per VA policy.

#### **5.4 Inclusion/Exclusion Criteria**

Our targeted range for the total number of study completions is up to 150.

##### **Inclusion Criteria:**

###### Control participants without OA: up to 30

1. age 18 to 80 years
2. able to stand and walk for about an hour (with breaks) and at least 15m (about 50ft) at a time without difficulty

###### Participants with ankle OA: w/varus ankle (up to 40); w/neutral ankle (40); w/valgus ankle (40)

1. radiographic evidence of tibio-talar ankle osteoarthritis (osteophytosis and/or joint space narrowing)
2. age 18 to 80 years
3. able to stand and walk for about an hour (with breaks) and at least 15m (about 50ft) at a time without difficulty

After consent, unless usable images are available, all participants will have a set of X-rays (foot and ankle, and long leg x-ray) in order to determine final group assignment and eligibility.

##### **Exclusion Criteria: all participants**

1. prior ankle joint replacement or fusion, or recent (<1 year) surgical, neurological, rheumatologic, or lower limb musculoskeletal problem (e.g., current foot ulcer, severe hip/knee OA, terminal illness, etc.) that impairs an individual's ability to do the walking tests
2. required use of upper extremity gait aid or orthotic device for walking
3. rapid onset of ankle OA (<3 years) following ankle fracture
4. diagnosis of severe ankle instability or deformity such as pes planus or knee varus / valgus deformity, visible during exam or present in long leg radiograph
5. inadequate cognitive function or language proficiency to consent or to participate
6. current incarceration
7. body mass index (BMI) > 40 kg/m^2
8. once an alignment type in the OA group (varus, neutral, valgus) has been filled, further potential participants of that population will be excluded
9. currently pregnant

##### **Additional Exclusion Criteria, Controls only:**

1. Ankle pain or ankle OA in addition to the above exclusionary criteria

## **5.5 Study Visits, Data Collection, and Risk Management**

All data collection procedures will be performed at the VA Puget Sound. There are several components to the study. Participants may be asked to complete some or all components of the study depending on their eligibility, but may do so over several visits (up to 4). We anticipate that most participants will complete all study components within 3 visits over a 3-4 month timeframe, but participant schedules and the accessibility of facility resources (i.e., the ability to schedule time slots with the Dept. of Diagnostic Imaging) may extend the study timeframe beyond this estimate. We will attempt to conduct multiple components of the study during each visit in order to minimize the number of visits required for participation. Visits may last up to 5 hours each. Study visits will be scheduled by contacting the participants on phone, or during in-person contacts. We may contact participants with appointment reminders via email or phone.

During study sessions, visitors and observers will not be allowed in the lab unless the participant agrees to their presence; the participant can change her/his mind at any time.

### **Photos and video**

We will also take video and photos of participants during portions of this study for documentation and use in research publications. All videos and photos will be taken from the neck down (to avoid facial identification) and without sound (to avoid voice identification), and tattoos and other distinguishing marks will be covered to protect the identity and privacy of our participants.

### **Eligibility Screening and Group Determination**

Participants will have been preliminarily screened during recruitment, then during the first visit, after informed consent is obtained, we will make a final eligibility determination. This will include verifying that the information collected during recruitment is accurate and current.

At each visit that involves exposure to radiation female participants of child-bearing potential (under age 50) will undergo a pregnancy test (urine test) so we can verify that they are not pregnant. Designated study staff will escort female participants to the bathroom and provide them with a specimen cup, pregnancy test strip, and a disposable container on which to place the used test strip. Staff will go over the test instructions, and verify the test result. Staff will not handle urine specimens, we will tell participants how to handle and dispose of the materials. If the test indicates that the participant is pregnant she will be not be able to participate in the study and we will advise her to see her regular clinical care provider. If a participant cannot continue in the study they will still be compensated for the visit.

Participants with ankle OA will be grouped based on their clinical diagnosis of ankle coronal plane alignment (varus, neutral or valgus) as noted in their medical record, and/or determined by reviewing/measuring ankle alignment in x-rays in the medical record during recruitment and screening. Participants with ankle OA who do not have a formal clinical diagnosis of alignment type, if

alignment type cannot be determined via the x-rays on file, or if there are no x-rays on file, will be categorized after undergoing the Standing Long Leg X-ray.

Participant weight and height will be measured, and his/her age, sex, race/ethnicity and Veteran status will be recorded. Participants will be asked to walk in a straight line in the hallway while a researcher times the subject to determine his/her natural walking speed.

### **Medical Record Review**

If participants have a VA or UW medical record we will check to see if they have already had a CT scan and/or X-rays (images) that can be used for this study. If participants report that they have had a CT scan and or X-rays at a different medical facility we may request copies of them. If possible, we will use the previously collected images for our data set and analyses so that participants do not have to be exposed to additional radiation. We will also access participants' medical records (at the VA Puget Sound or UW/Harborview Medical Center) to collect information related to their foot and/or ankle diagnosis and related clinical treatment. If participants' medical records are not at the VA they will be asked to sign a release form so that we can obtain copies of these records. After the release has been signed and delivered, the CT scans, X-rays and any other requested clinical notes from outside the VA will be delivered via the following methods:

- The images and other clinical treatment information may be burned to CD(s) or DVD by HMC or other facility and mailed to us via traceable shipping.
- A designated study staff member will pick up the CD(s) or DVD from HMC/UW or other facility and transport it to the VA.
- Information about lower extremity diagnoses and clinical treatment may be provided to designated study staff over the phone – the information will be labeled with the participants' study code and added to study records.

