### Biplane Fluoroscopy – Baseline

While wearing shorts (their own or ones we provide), participants will change into standard lab shoes and enter the Biplane Fluoroscopy Laboratory. Participants will step onto an elevated walkway, which is flat, about 3-feet wide, level, and has handrails on both sides. They will be asked to walk freely up and down the walkway to get comfortable with the test environment. External markers may be placed on the shoe for tracking purposes. While participants stand still on the platform, two fluoroscopes will capture simultaneous X-ray images of the participants' foot of interest, to record the standing position of the foot bones. These dual fluoroscopes allow for tracking of the bone motion in three dimensions (3D) while participants walk. Next, participants will be asked to walk along the platform while simultaneous X-ray images of the foot of interest are taken; each X-ray exposure is expected to last about 0.5 seconds, and will image from about 3 inches above the ankle to below the bottom of the shoe or foot. This set of standing and walking trials may also be

conducted with a neutral insert in the shoes, or barefoot. With some participants, we may capture images of each foot during the standing and walking X-ray procedures.

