## **5.6 Data Analysis**

### **Plan and Hypotheses:**

Hypothesis 1: During gait, there are different tibio-talar kinematics between OA participants with static varus alignment, OA participants with static valgus alignment, and controls.

Linear mixed effects regression will be used to test for differences in gait kinematic measures coronal plane alignment being the primary dependent variables by OA group (clinical OA varus, clinical OA valgus or controls, the independent fixed effects). Study subject will be modeled as a random effect. If the omnibus test for association between gait kinematic measure and OA group is significant, then pair-wise comparisons will be carried out.

Hypothesis 2: Some static neutrally aligned OA participants will exhibit varus or valgus tibio-talar misalignment when measured dynamically using biplane fluoroscopy.

To determine the potential miss-categorization of OA neutrally aligned participants: frequencies, percentages and 95% confidence will be estimated for the number of participants in the OA static (from standing radiograph) neutral group who are classified into varus, valgus or neutral using dynamic measures (from fluoroscopy trials).

Hypothesis 3: OA participants with static (varus/valgus) tibio-talar misalignment will exhibit reduced misalignment when walking with (lateral/medial) wedge insoles.

Linear mixed effects regression will be used to test for improvement in misalignment, i.e. the reduction in coronal plane disparity between OA and control participants (the dependent variable) when walking with a wedge vs. no wedge (the independent fixed effect) for OA varus and OA valgus participants separately. Subject and subject-x-wedge interaction (the latter to account for variability across multiple trials in the difference in within subject misalignment by wedge use) will be modeled as random.

Hypothesis 4: OA participants with static neutral alignment, but with dynamic (varus/valgus) tibio-talar misalignment will exhibit reduced misalignment when walking with (lateral/medial) wedge insoles.

This will be tested using the same methods as Hypothesis 3, substituting OA varus and valgus participants (from static radiographs) to those who are neutral in static radiography, yet varus or valgus dynamically.

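### The static class behind Hypothesis 2 may come from a chart label or an undated earlier film, so static-versus-walking disagreement can include elapsed time and inconsistent labelling

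*Combined protocol and SAP*

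**What the plan says.** The analysis plan and the enrolment text describe the static class differently.

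- **Section 5.6, Hypothesis 2.** The denominator is "the OA static (from standing radiograph) neutral group". These ankles are re-classed as varus, neutral or valgus from the walking fluoroscopy trials, and frequencies, percentages and 95% intervals are reported. Hypothesis 4 then tests insoles in the ankles that turn out discordant.
- **Section 5.5, Eligibility Screening and Group Determination.** OA participants are "grouped based on their clinical diagnosis of ankle coronal plane alignment (varus, neutral or valgus) as noted in their medical record" and/or by alignment "determined by reviewing/measuring ankle alignment in x-rays in the medical record during recruitment and screening". Those whose class cannot be settled in these ways "will be categorized after undergoing the Standing Long Leg X-ray". At the first visit, recruitment information is checked in general terms for accuracy and currency.
- **Section 5.4, inclusion criteria for OA participants.** "After consent, unless usable images are available, all participants will have a set of X-rays", and these determine final group and eligibility. What makes an image usable is not defined.
- **Section 5.5, Medical Record Review.** To limit radiation, "we will use the previously collected images for our data set and analyses" where possible, including images from other facilities.
- **Section 5.5, Biplane Fluoroscopy – Baseline.** Before the walking trials, a standing trial is taken "to record the standing position of the foot bones". Additional analysis 1 in section 5.6 compares peak gait misalignment with standing fluoroscopy in all groups.

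No section sets a maximum film age, states a loading requirement for filed images, or calls for a charted label to be re-measured.

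**The concern.** Three things can make the static and walking classes differ: the ankle changes in walking, it has changed since the film was taken, or the static label was produced in another way (a clinician's chart entry, a different view, a different reader). Hypothesis 2 is about misalignment that appears when alignment is measured dynamically, but the planned table cannot separate these sources.

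The second source is not far-fetched. The protocol's abstract says that injury may cause the joint to become misaligned over time. The third is recognised too: additional analysis 3 is planned because the clinical measure may depend on positioning.

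At stake are the Hypothesis 2 percentage and the make-up of the Hypothesis 4 group, which consists only of discordant ankles. Additional analysis 5, which compares statically and dynamically defined misalignment groups, is also affected.

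**Working it through.** **The plan's own figure.** The documents give no power or precision figure for Hypothesis 2. The only stated figure is power above 99% for the Hypothesis 1 comparison. It reproduces from the section 5.6 inputs (30 OA and 20 control participants, SDs 1.8 and 2.9, within-subject error 1.5, 3 trials, difference 3.5 degrees):

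- SE = sqrt((1.8² + 1.5²/3)/30 + (2.9² + 1.5²/3)/20) = sqrt(3.99/30 + 9.16/20) = 0.769
- Power = Φ(3.5/0.769 − 1.96) = Φ(2.59) = 99.5%

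That figure does not depend on the present point and is unaffected by it.

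**Illustration for Hypothesis 2 with no walking effect.**

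Inputs from the documents:
- Neutral band of 90 to below 100 degrees. This comes from a cited study in section 2.0; section 5.6 does not adopt it.
- Measurement error 1.5/sqrt(3) = 0.87 degrees, from the power paragraph, applied to every reading.
- Up to 40 neutral OA participants.

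Assumptions, not in the documents:
- An extra film-to-study discrepancy with SD s = 1, 2 or 4 degrees.
- True angles normal with mean/SD 88.8/6, 92/4 or 94.5/3. Section 2.0 cites the mean of 88.8 for end-stage OA; the other values are chosen.

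Model: film = T + D + e₁ and walking = T + e₂, with D ~ N(0, s²) and e₁, e₂ ~ N(0, 0.75). With f the density of T, the share called varus or valgus in walking among film-neutral ankles is

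∫ f(t) a(t)[1 − b(t)] dt / ∫ f(t) a(t) dt,

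where a(t) = Φ((100−t)/σ) − Φ((90−t)/σ) with σ = sqrt(s² + 0.75), and b(t) is the same expression with σ = sqrt(0.75). Setting s = 0 represents a same-session standing reference.

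| True angles (mean/SD) | Same-session | s = 1 | s = 2 | s = 4 |
|---|---|---|---|---|
| 88.8/6 | 9.6% | 12.3% | 17.9% | 30.2% |
| 92/4 | 7.5% | 9.1% | 12.2% | 18.7% |
| 94.5/3 | 4.0% | 4.4% | 5.2% | 7.0% |

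**Net of the same-session column:**
- s = 1: 2.7, 1.6 and 0.4 points, or 1.1, 0.6 and 0.2 of 40.
- s = 2: 8.3, 4.7 and 1.2 points, or 3.3, 1.9 and 0.5 of 40.

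**Systematic change.** If ankles had drifted 2 degrees towards varus since the film (92/4 case, s = 0), the share would be about 29% (11.5 of 40), against 7.5% without drift.

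**At least one of 40.** Hypothesis 2 says only that some participants will be discordant. With no walking effect, the chance of at least one is 1 − (1 − p)^40. That is about 80% at p = 4.0% and 98% at p = 9.6% with the same-session reference, and 83% to nearly 100% with the film. The existence of discordant ankles is therefore weak evidence either way; the percentage and its attribution carry the information.

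**Precision.** For 4 of 40 the exact 95% interval is 2.8-23.7%, and for 8 of 40 it is 9.1-35.6%. A random discrepancy of 1 degree would be hidden within such intervals. A 2-degree drift would not be negligible beside them.

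**The case against.** **Images, not labels, may settle the class.** Section 5.4 gives every participant X-rays unless usable ones exist and ties final assignment to them; section 5.6 says standing radiograph; section 5.5 requires a currency check. A reader might infer that films of any age or loading are accepted. The documents do not support that: on loading the enrolment text is silent, while section 5.6 points the other way. What stands is that nothing in sections 5.4 and 5.5 enforces the section 5.6 description, and that the grouping paragraph, as worded, lets a chart diagnosis suffice.

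**Disagreement with the clinical film is partly the question.** The abstract asks whether a single static clinical image is accurate enough, and Aim 2 concerns ankles currently classed as neutral. A reader might infer that all disagreement not caused by walking is contamination. That goes too far: a clinical film that misses misalignment is what Aim 2 looks for. Elapsed time and chart labelling remain a fair concern, because neither measures the accuracy of a standing film.

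**The standing trial is not ignored.** Additional analysis 1 already sets gait peaks against standing fluoroscopy in all groups. It is supplementary, however, and compares peak angles rather than classes, so it leaves the Hypothesis 2 table as it is.

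**Reusing images spares radiation.** This is a good reason to reuse films. It is not a reason to leave them undated or measured by mixed methods.

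**Conclusion.** The point holds as a gap between sections that should be closed. As written, the Hypothesis 2 share and the Hypothesis 4 population could include ankles that changed since the film or were labelled differently.

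The size cannot be stated from the documents. Under the assumptions above, 4.4-12.3% would be reclassified without any walking effect at an extra SD of 1 degree and 5.2-17.9% at 2 degrees, against 4.0-9.6% with a same-session reference. A reader might take the gross percentages as the bias. They are not: most of the SD 1 figure is error at the band edges, which remains under any reference, and the net excess is about 0-1 of 40 at SD 1 and 0.5-3 of 40 at SD 2. A larger or systematic discrepancy would matter more.

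The claim is that the result could be inflated, not that it will be.

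**What to change.** 1. Reconcile sections 5.4 and 5.5 with section 5.6. For analysis, measure every OA participant's static class by one study method on a standing film, either an existing one or the study film that section 5.4 already provides when none is usable. Do not take it from a chart label. Define usable, record film date and loading, and report the film-to-fluoroscopy interval.
2. State the cut-offs for Hypothesis 2.
3. Keep the film-based Hypothesis 2 table as primary, since Aim 2 asks what the clinical film misses. Beside it, cross-classify the same-session standing trial against the walking trials with identical cut-offs, extending additional analysis 1 from peak angles to classes. This separates discordance already present in standing from discordance that appears only in gait.
4. Do not remove ankles from the Hypothesis 2 numerator because of the standing trial. An ankle that the film missed and that is misaligned both standing and walking is a case Aim 2 seeks.

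**Cost and limits.** The cost is extra measurement work and occasionally a study X-ray where no standing film is on file; the standing trial adds no exposure. That trial is taken in lab shoes, with barefoot trials optional, so it supplements the clinical film and does not replace it. Its precision also matters: if the standing value had the full 1.5-degree error instead of 0.87, the same formula with σ = 1.5 for the reference gives 4.5-13.4% in place of 4.0-9.6%.
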